6.3 ATTRIBUTION OF TREATMENT-EMERGENT AE FOR INCOMPLETED AE DATE/TIME

AEs with incomplete start dates and times will be attributed to treatment according to the following algorithm:

1. Only the year is reported: If the year is after the year of the dose, the event will be considered as treatment-emergent. If the year is the same as the day of the dose, the event will not be considered as treatment-emergent.

2. Only the month and year are reported: If the month is after the month of the first dose, event will be considered as treatment-emergent. If the month is the same as the month of the first dose, the event will not be considered as treatment-emergent.
3. Only the time is missing: If the event occurred on or after the day of the first dose in the treatment period, then the event will be considered as treatment-emergent. Otherwise, the event will not be considered as treatment-emergent.

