9.1 ADVERSE EVENTS

All subjects in the Safety population will be included in the adverse event analysis.

AEs will be coded using the Medical Dictionary for Regulatory Activities (MedDRA) coding dictionary (Version 19.1 or higher)

An AE is defined as any untoward medical occurrence in a subject administered a medicinal product and which does not necessarily have to have a causal relationship with this treatment. An adverse event can therefore be any unfavorable and unintended sign symptom (for example, an abnormal laboratory finding), or disease temporally associated with the use of a medicinal product, whether or not considered related to this medicinal product. In clinical studies, an AE can include an undesirable medical condition occurring at any time, including baseline or washout periods, even if no study treatment has been administered.

In this study, all AEs that occur after any subject has been screened through the post-treatment follow-up period, whether or not they are related to the study, must be recorded on the eCRF, and must include the following: date and time of onset, date and time of resolution, severity, seriousness, causality (relationship to study medication), actions required, and outcome. Clinically significant and severe AEs must be examined to determine whether they meet criteria of a dose-limiting toxicity.

A treatment-emergent AE (TEAE) is any that is new in onset or was aggravated in severity or frequency following the first dose of study drug, up to and including the last visit of the study. Treatment emergence will be determined by comparing the AE start date/time with the actual date/time of first dose. In the case that the AE start date/time are incomplete, treatment emergence will be imputed according to the algorithm in SAP Section 6.5.

Adverse events will be listed chronologically by cohort/treatment, subject and AE start date/time. This listing will include all data collected in the eCRF, along with the derived variables: onset time since first dose, duration of AE and the coded variables system organ class (SOC) and preferred term (PT). Time since dose and duration will be calculated as described in SAP Section 6.3. In addition, serious AEs (SAEs) will be listed separately, if any occurs.

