The summary of AEs will be limited to TEAEs only. In cases where severity is missing for a TEAE, the TEAE will be considered to be the highest degree of severity: Severe. In cases where relationship information is missing for a TEAE, the TEAE will be considered to be reasonably related. Displays of TEAEs will include:

- Overall Summary of TEAEs

This table will include the number of events, number and percent of subjects who experienced TEAEs, serious TEAEs, severe TEAEs, related TEAEs and TEAEs leading to study discontinuation, summarized by treatment group.

- Summary of TEAEs by SOC, PT and Treatment Group

A summary of the number of events, number and percent of subjects who experienced at least one TEAE, as well as the number of events, number and percent of subjects who experienced each specific SOC, and PT will be presented by treatment group (including pooled placebo and pooled RP3128). If a subject has more than one occurrence of the same PT then the PT will be counted only once for that subject under the SOC at which it was experienced.

- Summary of TEAEs by SOC, PT, Treatment Group and Maximum Severity

A summary of the number and percent of subjects who experienced at least one TEAE by maximum severity as well as the number and percent of subjects who experienced each specific SOC and PT by maximum severity will be presented by treatment group. For this analysis, if a subject has more than one occurrence of the same PT, then the PT will be counted only once for that subject under the maximum severity at which it was experienced.

- Summary of TEAEs by SOC, PT, Treatment Group and Maximum Relationship

A summary of the number and percent of subjects who experienced at least one TEAE by maximum relationship as well as the number and percent of subjects who experienced each specific SOC and PT by maximum relationship will be presented by treatment group. For this analysis, if a subject has more than one occurrence of the same PT, then the PT will be counted only once for that subject under the maximum relationship at which it was experienced.

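### An AE whose partial start date matches the dosing month or year is classed as not treatment-emergent without any check, which drops most post-dose events with a missing onset day from the TEAE tables

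*SAP*

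**What the plan says.** SAP Section 6.3 gives three rules for incomplete AE start dates.

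- **Year only (rule 1):** a later year than the dose is treatment-emergent. Otherwise, "If the year is the same as the day of the dose, the event will not be considered as treatment-emergent". The wording compares a year with a day; I read it as the year of the dose.
- **Month and year (rule 2):** a later month is treatment-emergent. Otherwise, "If the month is the same as the month of the first dose, the event will not be considered as treatment-emergent".
- **Time only missing (rule 3):** "If the event occurred on or after the day of the first dose in the treatment period", the event is treatment-emergent.

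Section 9.1 defines a TEAE as an AE that is new or aggravated after first dose, up to the last visit. It sends incomplete dates to the algorithm ("treatment emergence will be imputed according to the algorithm in SAP Section 6.5"; the algorithm is in 6.3) and provides no override. It then states: "The summary of AEs will be limited to TEAEs only".

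Section 9.1 also fills in two other missing items: "In cases where severity is missing for a TEAE, the TEAE will be considered to be the highest degree of severity: Severe", and "In cases where relationship information is missing for a TEAE, the TEAE will be considered to be reasonably related". AE recording starts before dosing: "In this study, all AEs that occur after any subject has been screened through the post-treatment follow-up period".

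**The concern.** Rules 1 and 2 settle an uncertain onset against treatment emergence whenever the known part of the date matches dosing, and they use no other information. The post-dose period is only 15 days, so a genuine post-dose event will usually share the dosing month and almost always the dosing year.

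One case needs no probability. If the first dose is on the 1st of a month, an onset in that month cannot precede the dosing day. Rule 3 would accept such an event if its day were known; rule 2 rejects it.

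The direction also differs from the rest of the plan. Missing severity becomes Severe and missing relationship becomes related, but both defaults apply only to TEAEs, so an event removed under 6.3 never reaches them.

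Incidence of AEs is the first primary endpoint (Section 4.1). A removed event is absent from the overall, SOC/PT, maximum-severity and maximum-relationship tables. Active groups have 3 to 6 subjects, so a single event can move a row a long way.

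**Working it through.** The SAP states no figure on this point, so there is none to reproduce.

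**Inputs from the SAP.** Last visit is Day 15 (Appendices B and C). Confinement runs to Day 3 in SAD and Day 8 in MAD. Consent is at most 28 days before treatment in SAD (Appendix B), and screening at most 60 days before it in MAD (Appendix C). Group sizes are in Section 3.6.

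**Assumptions.** First-dose dates are spread evenly over 365 days (2017 calendar). Onset is even over the days stated.

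**Step 1: share of post-dose onset days that the rules reject.** Count pairs of dosing date and onset day in which both fall in the same month or year, and divide by all pairs.

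| Onset window | Same month | Same year |
|---|---|---|
| Days 1-15 | 4215 / (365 × 15 = 5475) = 77.0% | 5370 / 5475 = 98.1% |
| Days 4-15 (SAD, out of clinic) | 72.1% | |
| Days 9-15 (MAD, out of clinic) | 63.8% | |
| All onsets on Day 15 | 197 / 365 = 54.0% | 96.2% |

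The Day 15 row also means that for 54.0% of dosing dates all 15 days lie in one calendar month.

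The result depends on the dosing date. In a 30-day month with onset even over Days 1-15, the rejected share is 100% for doses on the 1st to 16th, 73% on the 20th, 53% on the 23rd, 47% on the 24th and 7% on the 30th. "Most" therefore fails only for cohorts dosed in about the last seven days of a month. Dosing on the 1st, where rejection is certainly wrong, is 12/365 = 3.3% of dates.

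**Step 2: the converse.** Of AE-days in the dosing month, what share is post-dose? With an even AE rate over the pre-dose window and Days 1-15, share = post / (pre + post).

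| Pre-dose window | Pre | Post | Post-dose share, same month | Post-dose share, same year |
|---|---|---|---|---|
| 1 day | 353 | 4215 | 92% | |
| 7 days | 2219 | 4215 | 66% | 68% |
| 14 days | 3850 | 4215 | 52% | |
| 28 days | 5348 | 4215 | 44% | 35% |
| 60 days | 5373 | 4215 | 44% | 21% |

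(Pre and post counts are for the same-month column.) If the AE rate doubles after dosing, the same-month share is 61% at 28 or 60 days, and the same-year share is 52% and 35%.

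**Step 3: effect of one dropped event.** If the subject has no other event in the row, the row falls by 1/n: 1/3 = 33 points (SAD 25 mg), 1/4 = 25 (SAD 50 and 100 mg), 1/6 = 17 (SAD 200 and 400 mg, each MAD dose), and 1/9 = 11 in pooled SAD placebo (1+2+2+2+2 = 9).

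**The case against.** The strongest reply is that the rule will seldom be triggered. Section 9.1 requires the date and time of onset for every AE. In MAD, Appendix C marks an AE check on every day from Day -1 to Day 13 and on Day 15, which leaves only Day 14. In SAD, confinement runs to Day 3, visits are on Days 5, 8 and 15, and there is a call three days before the last visit. A year-only onset inside these two weeks is hard to imagine, so the 98% describes a nearly empty set. This stands, and it limits the impact.

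The second reply is that the 77% is the wrong conditional. The default's error rate is the post-dose share among same-month events. That is 44% with the SAP's maximum windows, so under an even AE rate the default is right more often than wrong. If onset days are lost only on days without scheduled contact (a further assumption), the post-dose share is about 30% in SAD and 4% in MAD; with a 7-day pre-dose window it is about 53% and 10%. These figures are correct. Their spread shows that the month alone cannot classify these events. It does not justify ignoring the stop date and visit.

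Third, the severity and relationship defaults apply after treatment emergence is settled, and rule 3 works from a known day. That is fair: they show a different direction of caution, not a formal contradiction. The conflict with the TEAE definition in 9.1 remains.

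Finally, nothing is hidden. Every AE stays in Listing 16.2.7.1 with a TEAE flag, SAEs are listed separately, AE discontinuations are counted in Table 14.1.1, and no inferential AE test is planned. The 1/n steps are what any single AE does in groups this small. All true, but the summary tables would still be wrong for such an event.

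**Conclusion.** The concern holds and should be fixed. Applied as written, rules 1 and 2 misclassify genuine post-dose events against the plan's own TEAE definition, and do so with certainty when dosing falls on the 1st. With dosing dates and onset days spread evenly, they reject about 77% of post-dose AEs whose onset day is missing and about 98% of those with only a year.

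The error in these events can only lower reported incidence. The rule is the same in all arms, so the effect is on absolute incidence. Confidence is high on how the rule reads and on the calendar arithmetic. The total impact cannot be stated, because the number of partial dates is unknown and probably small.

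**What to change.** Replace rules 1 and 2 of Section 6.3 with: an AE whose partial start date is compatible with onset on or after first dose is treatment-emergent, unless the known part of the start date, the stop date or the recording visit shows that it began before first dose. Stop date and visit are already columns of Listing 16.2.7.1, so no new data are needed. The cost is SAP wording and one ADAE derivation.

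The downside is that some pre-dose events will be counted as TEAEs. Before the stop-date and visit check, and under an even AE rate, the pre-dose share of same-month AE-days is 34% (7-day window) to 56% (28- or 60-day window). For year-only dates it is 65% (28 days) to 79% (60 days). If pre-dose AEs are reported by the Day -1 check-in and carry that visit, about a one-day window is left and the same-month share falls to about 8%. That depends on how the visit is recorded, so check it against the eCRF completion guidelines.

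Two tidy-ups belong in the same edit but add no weight to this point. Correct the pointer in 9.1 from Section 6.5 to 6.3. Align the start-date-only test in 9.1 with its own definition, which includes worsening; whether a worsening gets its own record depends on the same guidelines.

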7 DEMOGRAPHIC, OTHER BASELINE CHARACTERISTICS AND MEDICATION

7.1 SUBJECT DISPOSITION AND WITHDRAWALS

For subject disposition, the following frequencies (number and percent) will be displayed by treatment group and overall for the randomized population:

- Subjects in the Randomized Population (number only)
- Subjects in the Safety Population (number only)
- Subjects in PK population
- Subjects who completed the study
- Subjects who discontinued early, as well as reasons for subject discontinuation

The denominators for the percent calculations will be the number of safety subjects per treatment group or overall.

A listing of randomization scheme will include the subject's identification, cohort, date of randomization, and treatment assignment.

Subjects' completion/discontinuation status will be listed by cohort/treatment and will include date of completion/early discontinuation, date of dosing and, for those who discontinued early, the specific reason(s) for discontinuation.

All deviations captured in eCRF will be listed. The list of protocol deviations will be reviewed by the Sponsor, the PI, the lead statistician and the study scientist and finalized before unblinding the treatment.

A listing of subjects excluded from the analysis populations will also be produced.

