5 ANALYSIS POPULATION

5.1 RANDOMIZED POPULATION

The randomized population consists of all eligible subjects who are randomized to receive a treatment regardless whether they are actually treated. These subjects are grouped by their randomized treatment group. The randomized population will be used to summarize subject disposition from randomization through termination.

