5.2 SAFETY POPULATION

The Safety population will include randomized subjects who receive at least one dose of study drug (RP3128 or placebo) during treatment phase. Subjects will be analyzed as treated, if any subjects received the study drug different from the drug they were randomized to receive. There will be separate safety populations each for SAD and MAD parts. The Safety population will be used for all analyses of safety endpoints, biomarker endpoints, as well as demographics and baseline characteristics.

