Note: Percentages are calculated based on the number of subjects in the Safety population per treatment group and overall.

**Table 14.1.2.S/M Summary of Demographics (SAD/MAD)
Safety Population**

	Pooled Placebo (N=xx)	RP3128 25 mg (N=xx)	RP3128 50 mg (N=xx)	RP3128 100 mg (N=xx)	RP3128 200 mg (N=xx)	RP3128 400 mg (N=xx)	All Subjects (N=xx)
Age (years)*							
n	xx	xx	xx	xx	xx	xx	xx
Mean	xx.x	xx.x	xx.x	xx.x	xx.x	xx.x	xx.x
SD	xx.xx	xx.xx	xx.xx	xx.xx	xx.xx	xx.xx	xx.xx
Minimum	xx	xx	xx	xx	xx	xx	xx
Median	xx.x	xx.x	xx.x	xx.x	xx.x	xx.x	xx.x
Maximum	xx	xx	xx	xx	xx	xx	xx
Sex, n (%)							
n	xx	xx	xx	xx	xx	xx	xx
Male	xx (xx.x%)	xx (xx.x%)	xx (xx.x%)	xx (xx.x%)	xx (xx.x%)	xx (xx.x%)	xx (xx.x%)
Female	xx (xx.x%)	xx (xx.x%)	xx (xx.x%)	xx (xx.x%)	xx (xx.x%)	xx (xx.x%)	xx (xx.x%)
...							

*Age at Informed Consent

Note: Percentages are calculated based on the number of subjects in the Safety population per treatment group and overall.

Programming Note: Table will also include race, ethnicity, height (cm), weight (kg), and BMI (kg/m2).

**Table 14.1.3.M Summary of Drug Administration (MAD)
Safety Population**

	Pooled Placebo (N=xx)	RP3128 25 mg (N=xx)	RP3128 100 mg (N=xx)	RP3128 400 mg (N=xx)
Number (%) of subjects who received all doses	x (xx.x%)	x (xx.x%)	x (xx.x%)	x (xx.x%)
Number of Days on Treatment				
n	xx	xx	xx	xx
Mean	xx.x	xx.x	xx.x	xx.x
SD	xx.xx	xx.xx	xx.xx	xx.xx
Minimum	xx	xx	xx	xx
Median	xx.x	xx.x	xx.x	xx.x
Maximum	xx	xx	xx	xx

**Table 14.2.1.1.X.S RP3128 Plasma Concentrations (ng/mL) by Time Point (SAD)
Safety Population
<Dose Level>**

Cohort /Subject	Time Point													
	0h	0.25h	0.5h	1h	2h	4h	6h	8h	12h	24h	48h	96h	168h	336h
xxxx	xxx.x	xxx.x	xxx.x	xxx.x	xxx.x	xxx.x	xxx.x	xxx.x	xxx.x	xxx.x	xxx.x	xxx.x	xxx.x	xxx.x
.....	xxx.x	xxx.x	xxx.x	xxx.x	xxx.x	xxx.x	xxx.x	xxx.x	xxx.x	xxx.x	xxx.x	xxx.x	xxx.x	xxx.x
Statistics														
N	xx	xx	xx	xx	xx	xx	xx	xx	xx	xx	xx	xx	xx	xx
Mean ¹	xxx.x	xxx.x	xxx.x	xxx.x	xxx.x	xxx.x	xxx.x	xxx.x	xxx.x	xxx.x	xxx.x	xxx.x	xxx.x	xxx.x
SD	xxx.xx	xxx.xx	xxx.xx	xxx.xx	xxx.xx	xxx.xx	xxx.xx	xxx.xx	xxx.xx	xxx.xx	xxx.xx	xxx.xx	xxx.xx	xxx.xx
CV (%)	xx.x	xx.x	xx.x	xx.x	xx.x	xx.x	xx.x	xx.x	xx.x	xx.x	xx.x	xx.x	xx.x	xx.x
Minimum	xxx	xxx	xxx	Xxx	Xxx	xxx	xxx	xxx	xxx	xxx	xxx	xxx	xxx	xxx
Median	xxx.x	xxx.x	xxx.x	xxx.x	xxx.x	xxx.x	xxx.x	xxx.x	xxx.x	xxx.x	xxx.x	xxx.x	xxx.x	xxx.x
Maximum	xxx	xxx	xxx	Xxx	Xxx	xxx	xxx	xxx	xxx	xxx	xxx	xxx	xxx	xxx

N= Number of subject for which plasma sample was collected at each time point.

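### Disposition counts randomized subjects but takes percentages of the safety population, so an undosed or mis-dosed subject makes the percentages invalid

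*SAP*

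**What the plan says.** Section 5.1 of the SAP defines the randomized population as "all eligible subjects who are randomized to receive a treatment regardless whether they are actually treated" and adds "These subjects are grouped by their randomized treatment group". It gives this population one task: "The randomized population will be used to summarize subject disposition from randomization through termination". Section 7.1 follows this, with frequencies "displayed by treatment group and overall for the randomized population", and the shell of Table 14.1.1 carries the same population in its title.

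The denominator comes from elsewhere. Section 7.1 says "The denominators for the percent calculations will be the number of safety subjects per treatment group or overall", and the note under Table 14.1.1 says "Percentages are calculated based on the number of subjects in the Safety population per treatment group and overall". Section 5.2 defines that second population: "The Safety population will include randomized subjects who receive at least one dose of study drug (RP3128 or placebo) during treatment phase". It is grouped by treatment received: "Subjects will be analyzed as treated, if any subjects received the study drug different from the drug they were randomized to receive".

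The rows shown with percentages are the PK population, completers, early discontinuations and each reason for discontinuation. The numbers randomized and in the safety population are shown as counts only.

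**The concern.** A percentage in a disposition table should be a proportion: everyone counted above the line should also be counted below it. Here the two can differ in two ways.

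- **Undosed subjects.** They belong to the randomized population, so they can enter the discontinued row, but they are not in the denominator.
- **Mis-dosed subjects.** They count in the numerator under the assigned treatment and in the denominator under the treatment received.

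In the first case the printed completion percentage is too high and the discontinuation percentage is not a proportion of any defined group. In the second, completion can exceed 100% in one column and fall short in another even though every subject completed. The groups are small, so a single case is plainly visible in a group column.

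**Working it through.** **Inputs.** Group sizes come from the cohort tables in Section 3.6, with placebo pooled across cohorts as Section 6.1 and the table shell require.

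- SAD active: 3 + 4 + 4 + 6 + 6 = 23. SAD placebo: 1 + 2 + 2 + 2 + 2 = 9. Total 32.
- MAD active: 6 + 6 + 6 = 18. MAD placebo: 2 + 2 + 2 = 6. Total 24.

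Both totals agree with the 32 and 24 in Section 3.5.

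**Assumption.** The SAP does not say how many subjects, if any, were randomized and not dosed. For illustration, take one such subject in the column considered, counted as discontinued early, with all others dosed as randomized and completing.

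**Formula.** Let n be the number randomized. Then n − 1 complete, 1 discontinues, and the safety count is n − 1.

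- SAP rule: (n − 1)/(n − 1) + 1/(n − 1) = n/(n − 1), which is above 100% for every n.
- Randomized denominator: (n − 1)/n + 1/n = 100%.

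| Column | n | SAP rule: completed + discontinued | Randomized denominator |
|---|---|---|---|
| SAD 25 mg | 3 | 2/2 + 1/2 = 150.0% | 66.7% + 33.3% |
| SAD 50 mg or 100 mg | 4 | 3/3 + 1/3 = 133.3% | 75.0% + 25.0% |
| SAD 200 mg or 400 mg; any MAD dose; MAD placebo | 6 | 5/5 + 1/5 = 120.0% | 83.3% + 16.7% |
| SAD pooled placebo | 9 | 8/8 + 1/8 = 112.5% | 88.9% + 11.1% |
| SAD total | 32 | 31/31 + 1/31 = 103.2% | 96.9% + 3.1% |
| MAD total | 24 | 23/23 + 1/23 = 104.3% | 95.8% + 4.2% |

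**Mis-dosing.** Suppose every SAD subject is dosed and completes, but one subject randomized to placebo receives 25 mg. Pooled placebo then reads 9/8 = 112.5% completed and 25 mg reads 3/4 = 75.0%. The SAD total stays at 32/32 = 100%, so this fault affects the treatment columns only.

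**No event.** If all subjects are dosed as randomized, the two denominators are equal in every column and the table is correct as planned.

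**The case against.** The strongest reply is that the fault may never show. The MAD schedule in Appendix C places randomization and first dosing on the same day, during confinement, and Section 7.3 has the drug taken at the site. An undosed subject is therefore unlikely, and the second route needs a dosing error. The table is descriptive, disposition is not an endpoint, and Section 7.1 and the table note agree, so a programmer meets no ambiguity. All of that stands, and it limits the importance of the point. It does not rescue the rule. The SAP itself provides for untreated subjects in Section 5.1, for mis-dosed subjects in Section 5.2 and for exclusions from the safety population in Listing 16.2.3. The denominator fails in exactly those cases.

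Four stronger readings are tempting, and the document does not support them.

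- **That losses before dosing are concealed.** Table 14.1.1 prints the randomized and safety counts in adjacent rows. Listing 16.2.1 gives dosing dates and discontinuation reasons, and Listing 16.2.3 gives reasons for exclusion. The smaller denominator also makes the discontinuation percentage larger, not smaller.
- **That every undosed subject pushes the sum above 100%.** This happens only if that subject is counted as discontinued early. Tabulating the randomized population through to termination implies it, but the SAP does not say so expressly. If the subject is in neither row, the sum is 100%, but the table no longer accounts for everyone randomized, which is at odds with Section 5.1.
- **That a cohort of 8 shows the size of the problem, with 7/7 + 1/7 = 114%.** Cohorts are not columns in this table. Placebo is pooled, and no planned column holds 8 subjects.
- **That every percentage in the table is wrongly based.** Section 5.3 makes the PK population a subset of the safety population, so the safety count is a coherent denominator for that row.

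**Conclusion.** The point holds as a conditional and minor error of specification. Section 7.1 and the Table 14.1.1 note pair numerators from one population with denominators from another, and the resulting percentages are invalid whenever a randomized subject is not dosed or receives the wrong treatment.

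For one undosed subject, completed plus discontinued ranges from 112.5% to 150% in the treatment columns and is 103.2% or 104.3% in the totals. These figures rest on the planned group sizes, on one undosed subject in the column, on counting that subject as discontinued early, and on all others being dosed as randomized and completing. Nothing in the SAP shows that either event occurred. The effect is confined to the disposition table, and no safety or PK result changes. The rule is still worth correcting, because it is fixed in both the text and the shell and will be programmed as written.

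**What to change.** In Section 7.1 and in the note under Table 14.1.1, make the number of subjects randomized, per treatment group and overall, the denominator for the completed, discontinued early and reason rows. The PK population row may keep the safety count, provided the note says so for that row.

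The cost is two wording edits and the matching change in the table program. No new data are needed, and the table is unchanged if all subjects were dosed as randomized.
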